2.0 Rationale and Specific Aims

The following hypotheses and specific aims were designed in response to a recent call from the American Heart Association (AHA) for i) standardized biomarkers to enable the clinical diagnosis of SSSB and ii) improved understanding of human tissue salt storage mechanisms²⁵.

Hypothesis 1: Tissue sodium content is elevated in adults predisposed for SSSB; tissue sodium and adiposity provide biomarkers for SSSB. **Aim 1:** Black adults without hypertension (20 male; 20 female) with BMI range=18 to 40 kg/m² and age range=18-55 years will be assessed for SSSB according to recent guidelines²⁶, and scanned using MRI to quantify tissue sodium and fat fraction in the lower extremities. Multivariable analyses will be applied to quantify relationships between tissue sodium, fat fraction as a surrogate of BMI, age, and sex with SSSB status. **Impact.** Unique tissue sodium and fat profiles may provide internal, mechanistic biomarkers of SSSB that could be used as endpoints in clinical trials of SSSB.

Hypothesis 2: Tissue sodium content is elevated in tissues affected by impaired lymphatic flow in adults with SSSB. **Aim 2:** The same participants will be scanned using noninvasive MR lymphangiography to quantify lymphatic flow velocity in the lower extremities. Non-parametric tests will be applied to evaluate the association between lymphatic flow and tissue sodium content in adults evaluated for SSSB. **Impact.** Identifying the extent of lymphatic dysfunction in SSSB could motivate novel treatment strategies to improve lymphatic pumping and tissue sodium clearance.

Hypothesis 3: Elevated tissue sodium content is associated with reduced renal perfusion in adults with SSSB. **Aim 3:** The same participants will be imaged using noninvasive MR spin-labeling techniques to measure kidney perfusion (ml blood/100g

tissue/min). Non-parametric tests will be applied to evaluate the association between kidney perfusion and peripheral tissue sodium content in adults evaluated for SSBP. Impact. Imaging of renal cortical circulation, where sodium-filtering nephrons are located, related to tissue sodium stores in SSBP may have potential to portend salt sensitive hypertension.

The overall goal of this work is to provide noninvasive imaging tools to assess a more complete spectrum of mechanisms underlying SSBP, which will motivate the use of these tools in future clinical trials to evaluate risk of SSBP or therapies to modify tissue sodium storage.

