Statistical analysis procedures for Aim 2: The primary statistical objective of Aim 2 is to test the hypothesis that tissue sodium content has an inverse relationship with lymphatic flow velocity, which depends on a person's salt sensitivity. To test this hypothesis, we will apply multivariable regression analysis using tissue sodium as the dependent variable, and lymphatic flow velocity, Δ MAP, biological sex, and age as independent variables among all participants.

Statistical analysis procedures for Aim 3: The primary statistical objective of Aim 3 is to test the hypothesis that elevated tissue sodium content is associated with reduced renal perfusion, which depends on a person's salt sensitivity. We will apply similar statistical analyses as Aim 2 to evaluate the relationships between renal cortical perfusion and peripheral tissue sodium content in adults evaluated for salt sensitivity.

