Statistical analysis procedures for Aim 3: The primary statistical objective of Aim 3 is to test the hypothesis that elevated tissue sodium content is associated with reduced renal perfusion in adults with SSBP. To test this hypothesis, we will calculate either the Pearson's- r or Spearman's-rho correlation coefficient, depending on normality, between renal cortical perfusion and peripheral tissue sodium content in adults who are SS or SR and matched for age, race, and BMI, and accounting for biological sex as a covariate. The correlation coefficient and adjusted p-values and 95% confidence intervals will be reported for each test. Based on our preliminary data in normotensive black women who display a Spearman's-rho=0.49 between tissue sodium and fat/water fraction (**Table 1**), we anticipate a similar or greater correlation with renal perfusion; with 20 subjects in each group, our design will provide 80% power to detect a correlation with two-sided significance of $p<0.05$ between tissue sodium content and renal cortical perfusion. Next, to compare the relationships in the SS group between i) tissue sodium and lymph flow velocity and ii) tissue sodium and renal cortical perfusion, a linear regression for each relationship with robust errors and an interaction term will be applied. The covariates will be biological sex and fat/water fraction. The coefficient for the interaction will be quantified as the difference between the slopes.

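### Aim 3's primary test is specified in three conflicting ways, and the protocol's pooled slope does not test the hypothesis in salt-sensitive adults

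*SAP*

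**What the plan says.** Three places describe the Aim 3 analysis.

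- **Protocol 2.0.** The hypothesis is "Elevated tissue sodium content is associated with reduced renal perfusion in adults with SSSB" (SSSB is the protocol's variant of SSBP, salt-sensitive blood pressure). The method is given as: "Non-parametric tests will be applied to evaluate the association between kidney perfusion and peripheral tissue sodium content in adults evaluated for SSBP".
- **Protocol 9.0.** The Aim 3 objective is an association "which depends on a person's salt sensitivity". For the method: "We will apply similar statistical analyses as Aim 2 to evaluate the relationships between renal cortical perfusion and peripheral tissue sodium content". The Aim 2 model has tissue sodium as outcome, with the flow measure, ΔMAP (the change in mean arterial pressure between diets), "biological sex, and age as independent variables among all participants". No interaction term is listed.
- **SAP 6.1, Aim 3.** The objective concerns adults with SSBP. The method is a Pearson or Spearman correlation "between renal cortical perfusion and peripheral tissue sodium content in adults who are SS or SR", "matched for age, race, and BMI, and accounting for biological sex as a covariate". The SAP claims 80% power with 20 per group at an anticipated correlation of 0.49 or more.

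The SAP then plans an interaction regression for Aim 3. It compares the lymphatic with the renal relationship inside the SS group, so it is neither a comparison of SS with SR nor the protocol's model. SAP 9.1, where the primary analysis should be defined, still holds template instructions.

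**The concern.** The specifications differ in who is analysed, what is estimated and which covariates are used. The same data could support Aim 3 under one document and not under the other, and nothing fixes the choice beforehand. The study is unblinded (SAP 6.3), so the choice could be made after results are seen.

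The protocol's model also has a problem of its own. A main-effects regression estimates one perfusion slope shared by everyone. Including ΔMAP as a covariate shifts the level of sodium but does not let the slope vary with salt sensitivity. The model therefore cannot show that the relationship depends on salt sensitivity, and it cannot isolate the relationship in SS adults. An association confined to SR adults could make the slope significant and be reported as support for a claim about SSBP.

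**Working it through.** **1. The SAP's own figure.** Inputs from SAP 6.1: correlation ρ = 0.49, n = 20 per group, two-sided 5%. With Fisher's z, power ≈ Φ(atanh(ρ)·√(n−3) − 1.960).

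- n = 20: atanh(0.49) = 0.536; 0.536 × √17 = 2.210; 2.210 − 1.960 = 0.250; Φ = 0.60. The stated 80% is not reproduced.
- n = 31: 0.536 × √28 = 2.837; Φ(0.877) = 0.81. At n = 30 it is just under 0.80, so about 31 are needed.
- ρ = 0.59, n = 20: 0.678 × √17 = 2.794; Φ(0.834) = 0.80.
- n = 40: 0.536 × √37 = 3.261; Φ(1.301) = 0.90. At ρ = 0.49 the pooled sample exceeds 80%; a group of 20 does not.

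**2. The specifications side by side.**

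| | Protocol 2.0 | Protocol 9.0 (via Aim 2) | SAP 6.1 |
|---|---|---|---|
| Test | Non-parametric | Regression slope | Pearson or Spearman correlation |
| Analysed | Adults evaluated for SSBP | All, pooled | SS and SR adults, sized per group |
| Adjustment | None named | ΔMAP, sex, age | Sex; matching on age, race, BMI |
| Varies with salt sensitivity? | Not stated | No term for it | Separate group estimates |

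**3. Association only in SR adults.** Assume N = 40 (both documents), ρ = 0.49 in SR and 0 in SS, and equal perfusion variance. The direction does not matter for a two-sided test. The SS:SR split is not fixed by design, so I use 20:20 (the SAP's figure) and 30:10 (the protocol's cited 74% prevalence × 40 ≈ 30). The common slope is roughly the size-weighted average of the group slopes.

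- 20:20: 20 × 0.49 / 40 = 0.245. atanh = 0.250; × √37 = 1.521; Φ(1.521 − 1.960) = 0.33.
- 30:10: 10 × 0.49 / 40 = 0.1225. atanh = 0.123; × √37 = 0.749; Φ(0.749 − 1.960) = 0.11.

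Simulation gives about 26–33% and 11–12% (10–12% across slightly different set-ups). The lower end at 20:20 arises when SS and SR adults also differ in mean sodium by the planned 6 with SD 4, that is 6/4 = 1.5 SD. The SS test stays at about 5%.

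**4. Association in SS adults (ρ = 0.49).** Simulation, 20,000 trials per setting, two-sided 5%. The protocol test is the perfusion coefficient adjusted for ΔMAP, sex and age. The SAP test is the SS correlation given sex.

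| SS:SR | ρ in SR | Sodium difference | Pooled slope significant | SS test significant | Exactly one significant |
|---|---|---|---|---|---|
| 20:20 | 0 | 0 | 32% | 60% | 36% |
| 20:20 | 0 | 1.5 SD | 27% | 60% | 41% |
| 20:20 | 0.49 | 0 | 89% | 60% | 32% |
| 20:20 | 0.49 | 1.5 SD | 81% | 59% | 30% |
| 30:10 | 0 | 0 | 63% | 79% | 22% |
| 30:10 | 0 | 1.5 SD | 56% | 79% | 28% |
| 30:10 | 0.49 | 0 | 89% | 80% | 13% |
| 30:10 | 0.49 | 1.5 SD | 82% | 80% | 15% |

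A further simulation put the range at about 11–42%. If the SS correlation is 0.59, it widens to about 5–47%. When the effect is confined to SS adults, the SAP test is usually the one that succeeds. When it is common to both groups, the pooled slope usually is.

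**The case against.** The best defence is that the documents are closer than they look. Protocol 9.0 says similar, not identical, analyses, and its objective says the relationship depends on salt sensitivity, so an interaction may have been intended. The SAP's objective names adults with SSBP, and for Aim 2 it expects significance in SS but not SR adults, which suggests that the SS result decides Aim 3 too. Spearman's correlation would satisfy Protocol 2.0. Where the association is the same in both groups, disagreement mainly reflects 40 against 20–30 participants, not a wrong scientific answer. The SR-only case also runs against the stated hypotheses.

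Much of this stands. It would overstate the matter to say that the SAP gives no hint of which group counts, and the common slope is the literal reading of Protocol 9.0, not a stated intention. But an unstated interaction is not a specified one, the Aim 2 expectation is not repeated for Aim 3, and no rule ranks the documents. The SR-only case still shows what the pooled slope cannot rule out.

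A reader might also infer that three candidate results (SS, SR, pooled) more than double the false-positive rate. The documents do not support that. Neither plans to claim success if any of the three is significant, and the SAP says "The correlation coefficient and adjusted p-values and 95% confidence intervals will be reported for each test". It names no method, but a simple Bonferroni adjustment of its two correlations would hold the rate near 5%.

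**Conclusion.** The point holds. Aim 3 has three conflicting specifications of its primary test and no statement of which governs. The Protocol 9.0 model, as listed, tests neither its own objective nor the SSBP hypothesis.

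The percentages are illustrations. They rest on N = 40, a correlation of 0.49 (which the SAP borrows from sodium against fat/water fraction), an assumed SS:SR split, normal data and an assumed SS/SR sodium difference. A reader might take 11–42% as a limit on the disagreement, or as trials with opposite signs. It is neither: it counts trials in which one test is significant and the other is not, and it moves with every assumption above.

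The power finding is firmer. At the SAP's own inputs, 20 SS adults give about 60%, not 80%. Twenty SS adults are not guaranteed either, because salt sensitivity is known only after both diets.

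**What to change.** State one decisive Aim 3 test in the same words in Protocol 2.0, Protocol 9.0 and SAP 6.1, before perfusion and sodium are analysed by SS status:

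- **Model:** all participants; tissue sodium on perfusion, SS status, perfusion × SS status, and one agreed covariate list such as sex and age. Leave ΔMAP out, because SS status is derived from it.
- **Decisive test:** the perfusion slope in the SS group, two-sided 5%.
- **Secondary:** the interaction (SS slope minus SR slope, with 95% CI), which addresses the protocol's wording that the relationship depends on salt sensitivity.
- **Descriptive:** the SR and pooled slopes with 95% CIs and no claim.
- **Power:** replace the 80% statement. At 0.49 and 20 SS adults it is about 60%; 80% needs about 0.59 at that size, or about 31 SS adults.

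The cost is wording in two documents and no new data. The price is power. At 20:20 and 0.49 the SS slope from this model has about 57–62%, against 81–89% for the pooled slope if the association is the same in both groups. The interaction is weaker still. At 20:20 with no SR association its standard error is about √2 times that of the SS slope, so 2.210/1.414 = 1.563 and Φ(1.563 − 1.960) ≈ 0.35. If the sponsor prefers a different contrast, it should still name one, with its analysis set, covariates and success rule, and reword the hypothesis to match.

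### SAP Aim 3 compares the lymphatic and renal links to sodium by subtracting slopes in different units, and the Protocol 9.0 model cannot test the salt-sensitivity dependence it states

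*SAP*

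**What the plan says.** **SAP Section 6.1, Aim 3.** The main analysis is a correlation "between renal cortical perfusion and peripheral tissue sodium content in adults who are SS or SR" (salt-sensitive or salt-resistant). A second step then aims "to compare the relationships in the SS group between i) tissue sodium and lymph flow velocity and ii) tissue sodium and renal cortical perfusion". It fits one linear regression per relationship, with robust errors, an interaction term, and sex and fat/water fraction as covariates. The result is defined as follows: "The coefficient for the interaction will be quantified as the difference between the slopes". The same closing sentence appears under SAP Aim 2, where the interaction is between lymph velocity and SS/SR group.

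**Protocol Section 2.0.** The two measures are on different scales. Aim 2 uses "noninvasive MR lymphangiography to quantify lymphatic flow velocity in the lower extremities". Aim 3 uses "noninvasive MR spin-labeling techniques to measure kidney perfusion (ml blood/100g" tissue/min). Hypothesis 3 is worded as an association: "Elevated tissue sodium content is associated with reduced renal perfusion in adults with" salt-sensitive blood pressure.

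**Protocol Section 9.0.** For Aim 2 the hypothesis is that "tissue sodium content has an inverse relationship with lymphatic flow velocity, which depends on a person's salt sensitivity". The model regresses tissue sodium on "lymphatic flow velocity, Δ MAP, biological sex, and age as independent variables among all participants". Aim 3 states the same kind of dependence for renal perfusion and says similar analyses will be used. No product term is listed for either aim.

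**The concern.** There are two related faults.

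(a) A regression slope carries the units of its predictor. Subtracting a slope per unit of velocity from a slope per unit of perfusion gives a number with no fixed meaning. It is not zero when the two associations are equally strong, unless the two SDs happen to be numerically equal. Separate regressions within one group also contain no interaction term. A stacked model could supply one, but each person then appears twice with the same sodium value, and the SAP does not say how that is handled. The step could report that the lymphatic and renal links differ when they do not, or miss a real difference, for reasons of unit choice alone.

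(b) A main effect of ΔMAP tests whether mean sodium shifts with salt sensitivity. It does not test whether the slope of sodium on flow changes with salt sensitivity, which is what Protocol 9.0 states. The SAP has the needed interaction for Aim 2, so the two documents give different Aim 2 models. For Aim 3 neither document has a formal between-group test: separate correlations in SS and SR do not compare the groups.

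**Working it through.** **Inputs from the documents.** Planning correlation 0.49, 20 per group, two-sided 5% (SAP Aim 3); sodium SD 4 mmol/L (from the 6 ± 4 in SAP Aim 1); total 40.

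**Assumed, because the documents give no values.** SD of velocity 0.3 cm/min; SD of perfusion 40 ml/100 g/min; correlation between the two predictors 0.2. The sign is taken as negative, as hypothesised.

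**The plan's own figure.** The only figure in the Aim 3 text is 80% power for a correlation of 0.49 with 20 subjects. By Fisher's z: atanh(0.49) × √17 − 1.960 = 0.536 × 4.123 − 1.960 = 0.25, which gives 60%. The 80% is not reproduced, but that is a separate matter and nothing below depends on it.

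**(a) Step 1, algebra.** A slope is b = r × SD(sodium) / SD(predictor). If both correlations equal r, the slope difference is r × SD(sodium) × (1/SD₁ − 1/SD₂). This is zero only if SD₁ = SD₂ as numbers.

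**Step 2, numbers.**
- Velocity: −0.49 × 4 / 0.3 = −6.53 per cm/min.
- Perfusion: −0.49 × 4 / 40 = −0.049 per ml/100 g/min.
- Ratio 133, so the difference is almost the velocity slope alone.
- Perfusion per g (SD 0.4): −0.49 × 4 / 0.4 = −4.9, close to −6.53. The data are the same and the answer changes.

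The sign can change too. With assumed SDs of 0.2 and 50, perfusion slope minus velocity slope is −0.039 + 9.8 = 9.76. If the velocity values are multiplied by 600 (SD 120), it is −0.0392 + 0.0163 = −0.023.

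**Step 3, simulation.** Two stacked rows per person; terms for relationship, predictor, their product, sex and fat/water fraction; errors clustered by person; 4,000 runs. The table gives how often a difference is declared, with jackknife (CR3) then CR1 errors.

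| Case | n = 20 SS | n = 24 | n = 30 |
|---|---|---|---|
| Equal associations, raw units | 49%, 62% | 59%, 69% | 72%, 80% |
| Equal, perfusion per g | 6%, 11% | – | – |
| Real difference (lymph 0, renal −0.49), raw | 4%, 8% | 5%, 8% | 4%, 7% |
| Equal, z-scored predictors | 2%, 6% | – | 3%, 6% |
| Equal, dependent-correlation test (Williams) | 5% | 5% | 5% |

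The third row follows from the scale. The true difference is 0.049, while the standard error of the velocity slope is roughly 4 / (0.3 × √20) = 2.98. Over SDs of 0.1–0.6 and 20–80 at n = 20, the raw-unit rates are 47–51% (jackknife) and 61–63% (CR1). With perfusion per g they run from 6% to 55%.

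**(b) Main-effects model, 20 SS and 20 SR, standardised units.**

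| Truth | Average flow slope (significant) | Salt-sensitivity main effect | Added product term |
|---|---|---|---|
| Slope −0.56 in SS, 0 in SR | −0.28 (35%) | 5% | 36% |
| Slope −0.28 in both | −0.27 (36%) | 5% | 5% |

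The main-effects fit looks the same whether or not the relationship depends on salt sensitivity. Only the product term separates the two.

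**The case against.** - **Another reading of the SAP.** Because the Aim 3 wording mirrors Aim 2, the step might mean one regression per relationship, each with an SS/SR term. The text is loose, but it confines the comparison to the SS group, where no SS/SR term can exist. This reading does not stand.
- **Scaling may be intended.** The SAP does not say the slopes are raw. It states no common scale either, and in an unblinded study that choice should not wait until results are seen.
- **The rejection rates come from a stacked model that the SAP does not write down, and the step states no test.** This is true, and the raw slopes really do differ, so these are not false positives in the strict sense. The fault is a quantity that does not answer the question. Step 1 shows it without any simulation.
- **The percentages move.** This stands. With velocity in cm/h the equal-association rate at n = 20 is 21–31%. With the SAP's own 0.49 correlation between sodium and fat/water fraction built in, it is 64–77%. The figures are illustrations.
- **Part (b) is partly covered, and the Aim 3 step is secondary.** SAP Aim 2 does have the interaction, so for Aim 2 the task is to reconcile the documents. The Aim 3 comparison is a follow-on step with no power claim of its own. Both points limit the severity but remove neither fault.

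**Conclusion.** The concern holds on both parts and should be corrected before analysis. The Aim 3 slope difference is wrong as written: its size, sign and significance depend on units. That conclusion is algebraic and needs only the two measures to have different units. The illustrated size (49–62% declared differences under equal associations at n = 20, and 4–8% detection of a real difference at n = 20–30) rests on the assumed SDs, units and predictor correlation, on covariates unrelated to sodium, and on a person-clustered stacked model. Protocol 9.0 states a dependence on salt sensitivity for Aims 2 and 3 that its own model cannot test. This takes its wording to mean a change in slope, which SAP Aim 2 supports by expecting a significant relationship in SS but not in SR.

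**What to change.** **(a) SAP Aim 3.** Keep the marginal comparison within the SS group, but replace the raw slope difference with one of these:
- a test of two dependent correlations that share tissue sodium, partial on sex and fat/water fraction, with a bootstrap over persons if Spearman is used; or
- z-scored predictors in a stacked model with errors clustered by person, naming the variance estimator.

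If both z-scored predictors go into one model instead, state that the comparison is then mutually adjusted.

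**(b) Protocol 9.0 and SAP.** Add the salt-sensitivity interaction to the protocol's Aim 2 model, in line with SAP Aim 2. State one form of the modifier: the protocol uses continuous ΔMAP, the SAP uses SS/SR. For Aim 3, either add the same interaction in both documents, or reword Protocol 9.0 to the association in Protocol 2.0 and the SAP and claim no dependence.

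**Cost.** Wording only; no new data. Power is low and should be stated. For −0.49 against 0:

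| Method | n = 20 | n = 24 | n = 30 |
|---|---|---|---|
| Dependent correlations | 37% | 48% | 58% |
| z-scored stacked, jackknife | 18% | 28% | 43% |
| z-scored stacked, CR1 | 33% | 42% | 55% |
| One model, both predictors | 28% | 38% | 50% |

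With the 0.49 sodium–fat/water correlation included, the z-scored stacked model has about 28–44% at n = 20. The SS/SR interaction has about 19–35% power (−0.49 in SS against an assumed 0 in SR, by method and split). Estimates with confidence intervals should therefore lead the report. Standardised measures also depend on each measure's spread and reliability in the SS group, and the SAP should say so.

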6.3 Randomization and Blinding

All subjects will undergo the same interventions. However, the order of the study interventions will be randomized using a randomized crossover design.

This is not a blinded study.

6.4 Study Assessments

| Visit | Screening | Baseline | Diet 1 | Washout | Diet 2 | MRI |
|--------------------------|-----------|----------|--------|---------|--------|-----|
| Target day of visit | | 1 | 7 | 14 | 21 | 28+ |
| Phlebotomy | X | X | X | X | X | |
| 24-hour urine collection | | X | X | X | X | |
| MRI | | | | | | X |
| History & Physical | X | | | | | |
| Study Diet | | | X | | X | |
| Pregnancy test | X | | | | | |
| Biophysical exam | | X | X | X | X | X |
| Adverse event monitoring | | X | X | X | X | X |

